6.5. Concomitant Medications

Non-enzyme inducing anticonvulsants may be given as clinically indicated. Enzyme inducing anticonvulsant agents should be avoided if possible. See Appendix 5 for a list of the enzyme inducing anticonvulsant agents.

During the trial, corticosteroids may be given as clinically indicated in the lowest possible dose per treating physician discretion. However, if the dose of steroids is increased while on therapy due to worsening of neurological symptoms, MRI of primary tumor is recommended to evaluate for disease status.

Acetaminophen and NSAIDS (ibuprofen, naproxen) may be given as needed to control poly-ICLC side effects. Use of ibuprofen or other NSAIDS during thrombocytopenia less than 50,000 /mm³ should be avoided. Other instructions on the use of NSAIDS in this setting will be per treating physician discretion.

Vitamins at the daily recommended dosage are allowed while on study treatment. Other supplements, including cannabidiol-containing compounds, are not recommended.

For additional information on concomitant medications, see Investigator Brochure.

Radiotherapy or other-directed tumor therapy are not allowed in the trial.

Appropriate antibiotics, GCSF (Granulocyte Colony Stimulating Factor), blood products, antiemetics, fluids, electrolytes and general supportive care are to be used as necessary and as per institutional guidelines.

PJP (formerly PCP) prophylaxis will be given following institutional guidelines based on absolute lymphocyte count.

Given the risk of intratumoral hemorrhage with thrombocytopenia, a platelet transfusion should be considered if the platelet count is < 25,000/mm³. Higher transfusion parameters may be used if clinically indicated. All blood products will be leukocyte depleted and irradiated to prevent graft-versus-host disease.

Influenza vaccine administration: Inactivated Influenza vaccine can be given to patients on study, but it is recommended that it not be given the same day as study drug.

Other vaccinations must be approved by the Protocol Chairs.

6.6. Toxicity

See the current Investigator's Brochure for a complete list of expected toxicities.

1. Discomfort at IM injection site: The most common adverse effect is mild, transient discomfort at the site of IM injection. With subcutaneous (SC) injections, there is a transient mild to moderate grade 1 or 2 erythematous skin reaction.³

2. Flu-like symptoms: Approximately 8 to 12 hours after doses of 10 to 50 mcg/kg IM, patients may develop a mild flu-like syndrome with fever of less than 39 °C, which may last for about 12 hours, but responds readily to acetaminophen or ibuprofen. Mild myalgia, arthralgia, sometimes nausea, and malaise can be present during this period. This flu-like syndrome typically diminishes markedly after the first few poly-ICLC treatments. On rare occasions in the course of treatment, patients who have been tolerating treatment uneventfully may develop an earlier, more pronounced fever with chills and malaise (typical of higher dose IV poly-ICLC) in response to an IM injection. This will typically resolve over 12 to 24 hours, responds to acetaminophen, and does not typically recur on subsequent dosing.

3. Hematologic abnormalities: Several cases of transient leukopenia have been reported at higher doses. High dose Poly-ICLC has been associated with a coagulopathy in dogs, but not in other species including primates. There has been no change in the expected incidence of deep venous thrombosis, pulmonary embolus, or coagulopathy in multiple sclerosis, AIDS or malignant glioma patients on low dose IM poly-ICLC. One paralyzed multiple sclerosis patient treated with 100 mcg/kg IV suffered a fatal pulmonary embolus, which was not judged to be due to the drug.

4. Hepatic enzyme elevation: Mild and typically transient hepatic enzyme elevation has been described in poly-ICLC when given intravenously at doses from 20 to 100 mcg/kg. Preclinical studies have shown increased hepatic NK cells, as well as suppression of the P450 hepatic enzyme system by poly-ICLC, but the clinical implications of this finding are not clear.

5. Seizures: Seizures during high febrile episodes have been reported with glioma and known seizure disorder.

6. Diarrhea: Grade 1-2 diarrhea has been reported in brain tumor patients receiving IM Poly-ICLC two to three times weekly for months.

7. Tuberculosis (TB) in Mice: Mouse studies have reported a risk of worsening of TB in mice already infected with TB that are treated with Interferon or with poly-ICLC. Temporary worsening of TB has also rarely been reported in patients treated with high doses of interferon.

8. Transient anaphylactic reaction: There have been reports of transient anaphylactic reaction to the combination of a personalized glioma vaccine, GM-CSF, and poly-ICLC in glioblastoma patients. GM-CSF is known to cause anaphylaxis, but there have been no previous such reports in patients receiving poly-ICLC alone or with other vaccines.

9. Transient peritumoral edema: In a pilot brain tumor trial, a few patients showed an increase in gadolinium enhancing lesions after 3 - 6 months of IM poly-ICLC, followed by an apparent tumor response at 6 - 12 months and prolonged survival on continued treatment. Dexamethasone was used as needed in the first few months of treatment on that study. In a more recent follow-up open study in patients with advanced recurrent gliomas, several patients have shown increased peritumoral edema after several weeks of poly-ICLC therapy. This has resolved in all cases on continued poly-ICLC, with or without concomitant steroids. Biopsy data in at least two patients treated with poly-ICLC also showed a peritumoral inflammatory response. Likewise, in a dendritic cell vaccination trial in recurrent glioma patients with twice-weekly application of poly-ICLC IM, remarkable post-vaccination immune cell infiltration into the tumor was seen. These findings are commonly reported with other immunotherapies, and they raise the possibility that poly-ICLC may at times be facilitating a relatively early immunologic response to the tumor, perhaps manifested by transient increased edema or gadolinium enhancement. In line with this, one case of post-vaccination brain edema (Grade 3) possibly related to poly-ICLC adjuvant vaccination of a multi-peptide vaccine was reported from a Phase I trial in glioblastoma.

7. BIOMARKER, CORRELATIVE, AND SPECIAL STUDIES

This protocol involves extensive correlative studies to gain fundamental insights into the effects of poly-ICLC on the circulating immune cells and whenever possible tumor infiltrating immune cells. The proposed studies may help understand correlates of response in NF1 patients with LGG who are treated with poly-ICLC.

[figure not shown]
Specimens:

Both blood and tissue specimens (if available) will be analyzed.

Time-points for mandatory biological studies:

Baseline; cycle 1 day 8 and day 15; day 1 of cycles 3, 6 and 12; and at end of therapy or progression. Additional samples will be collected at 3 time points when participant is off therapy: 3 months, 12 months and at the time of progression. See Appendix 6. We will collect 5-10ml of blood per sample in sodium heparin tubes for patients < 8 years of age. For patients that weigh less than 10 kg, collect 2 ml on cycle 1 day 8. For patients \geq 8 years, we will collect 10-15 ml. Biological samples should be drawn within 24 hours prior to the next study dose (when applicable) whenever possible. **No biological samples should be drawn on a Friday. Samples should be shipped at room temperature. Biological samples should not be obtained through a finger stick. These samples will be processed at Emory University.**

Figure 6: Research Sample Collection Schedule

Mandatory Biological Specimens

Single cell mass cytometry or CyTOF will be used for phenotypic characterization of circulating as well as tumor infiltrating immune cell populations, using a 36-marker panel that we have developed. **Fig 5** shows enrichment of myeloid cells within glioma tumor tissue using multi-parameter analytic platforms such as t-SNE, which can be utilized to analyze mass cytometry data.

Functional assays: We will perform T cell proliferation as well as characterize cytokine secreted by T cells before and after poly-ICLC therapy. We are particularly interested in understanding the changes in antigen specific T cell responses which has been shown to be important for glioma initiating/stem cells.

Multiplex Luminex ELISA: We will assess changes in plasma cytokine milieu, including circulating cytokines IL6 and TNF α .

Optional Pre and post treatment tissue and blood samples:

When available, fresh frozen and/or FFPE tumor sample is requested (either from surgical resection within 6 months prior to enrollment, during study therapy and/or progression). Blood sample will be collected at the time of surgical resection. These samples will be stored in a tissue bank located at Children's Hospital of Philadelphia for future use studies. See Appendix 7.

Tumor and Blood samples left over from the biological correlates drawn at any of the above time points may be banked for future research.

8. QUALITY OF LIFE (QOL) STUDIES AND NEURO-COGNITIVE BATTERY

Brief Background: Mounting literature suggests that pediatric cancer survivors are negatively affected by persisting and clinically significant late-effects due to cancer and its treatment. Compared to other diagnoses, CNS-tumor survivors are at highest risk for neurocognitive, psychological, cardiopulmonary, endocrine, and musculoskeletal complications and second malignancies. Only limited data describe pediatric LGG and/or NF outcomes, despite their

prevalence.³⁸⁻⁴¹ Extant research describes HRQOL impairments for adults with a LGG^{39,40} and, while not methodologically robust (i.e., small sample size, retrospective design, lack of validated PROs), preliminary research in PLGG survivors provides evidence of cognitive decline, learning disability, and adjustment difficulties following treatment.⁴¹⁻⁴⁵ For youth with refractory or progressive pediatric brain tumors especially, longer life may come at significant cost in morbidity and health-related quality of life (HRQOL). Use of both patient-reported outcomes (PROs), data collected "directly from the patient, without interpretation of the patient's response by a clinician"⁴⁶ and objective performance-based measures to monitor potential neuro-toxicity are critical to understanding the impact of new treatments on a child's general functioning. Novel treatments that increase survival while also maintaining HRQOL are highly desirable.⁴⁷⁻⁵⁰

Diagnosis and subsequent treatment may result in impaired neurobehavioral functioning or, given its relatively encouraging prognosis, may not result in adverse outcomes directly. Rather, as suggested by the Human Evolutionary Response to Trauma/Stress (HEART) model,⁵¹ insult to the child's developing nervous system (i.e. as measured by the parent proxy reported executive functioning measure) may moderate the relationship between diagnosis/treatment and long-term functioning (Figure 7). Guided by the HEART theoretical model, a complementary battery of measures was selected whereby the patient is embedded within the family and larger social systems.⁵² Given a growing literature suggesting a cancer diagnosis may also result in growth/positive adjustment, measures of both negative and positive psychological functioning were selected. Factors have broad support in previous literature and are highly salient to existing interventions.⁵³⁻⁵⁵ In the event the cognitive battery or self-report PRO battery cannot be completed due to intellectual disability (i.e., known IQ ≤ 70 by medical record review), informant PRO measures will still be completed. Measured constructs and their corresponding measure are briefly described in Table 6. All measures are psychometrically sound; appropriate validity, reliability, and normative data is available for all ages proposed.

[figure not shown]
8.1. Patient Reported Outcome Battery

Children and adolescents will complete a PRO measurement battery (by patient age; Table 7) prior to first dose at treatment initiation, cycle 6, cycle 12, end of treatment (cycle 24) or progression and when applicable, at 24 months post completion of therapy (+/-5 days). Of note, safety and suicidal ideation will not be assessed; however, negative affect items will be reviewed, and each site notified of elevated scores. A trained study team member (supervised by a licensed clinical psychologist) will be available to assist younger children with PRO questionnaire completion as needed.

Time to complete the complete the PRO battery (treatment initiation, cycle 6, cycle 12, cycle 24 or time of progression, 24 months post completion of treatment) varies by age: Young Child (3-7y) = 0 minutes; Child (8-17y) = 27-37 minutes; Adult (≥ 18 y) = 32-42 minutes, Parent/Informant = 35 minutes. The demographic questionnaire (5 minutes) will be completed at baseline only by adult patients and parents/informants.

PROs will be administered via paper form, iPad using the NIH Toolbox App and the eDCS, a secure, web-based application designed to support data capture for research studies. Similar to other data collection programs, both eDCS and the NIH Toolbox App provide a questionnaire response system designed to collect sensitive information to reduce social desirability.⁵⁸

Figure 7: HEART Model, Adapted

Participant responses are entered directly into the computer program, minimizing data entry errors and/or multiple responses to items. This method of measure administration has been used successfully in other pediatric research protocols at pediatric institutions.

Table 6. Patient-Reported Outcome Battery by Age (years)

CONSTRUCT	CHILD: 8-17	YOUNG ADULT: ≥ 18	PARENT/INFORMANT (of all patients)
HRQOL	Pediatric Quality of Life Inventory (PedsQL 4.0) : physical, emotional, social, and school/work HRQOL; self- and proxy report		
Executive functioning	—	—	Behavior Rating Inventory of Executive Function (BRIEF-2) : inhibit, plan/organize, emotional control, working memory, organization, etc.
Negative Affect	PROMIS Depression, Anxiety, Anger : fear, sadness, anger; self- and parent proxy report (CAT)		
Psychological Well-Being	PROMIS Positive Affect, Life Satisfaction : positive affect, life satisfaction; self- and parent proxy report (CAT)		
Stress & Self-Efficacy	PROMIS Stress Experiences/Psychosocial Impact and Self-Efficacy perceived stress, self-efficacy; self- and parent proxy report (CAT)		
Social Relationships	PROMIS Peer and Family Relationships/Companionship and Emotional Support social support, companionship, social distress; self- and parent proxy report (CAT)		
Fatigue	PedsQL Multidimensional Fatigue Scale : general fatigue, sleep and rest fatigue, cognitive fatigue; self- and proxy report		
Adverse Symptoms	Patient-Reported Outcomes version of the Common Terminology Criteria for Adverse Events (PRO-CTCAE™) : NCI patient-reported outcome measure of adverse events in patients on clinical trials		
Social Attainment	—	Demographic Questionnaire : will collect information re. socio-demographic status, education/vocational attainment, independent living, Supplemental Security Income (SSI), supportive services, etc. Baseline only	

Note. Items for PROMIS scales will vary; computer adaptive testing (CAT) will be utilized to minimize the number of items required to be completed.

***IMPORTANT ADMINISTRATION GUIDELINES:** English and Spanish translations of all measures below will be utilized. There are different PRO forms based on patient age as described below. The participant will complete the questionnaire according to the age they are on the date of survey completion.

PedsQL 4.0 Core Scale and PedsQL Multidimensional Fatigue Scale. For this study, patients 8-25 years old will complete the PedsQL *self-report* measures. Parents or informants of patients 2-25 years of age will complete the PedsQL *parent proxy report* measures. Parents/informants will complete proxy forms by the following patient age: toddler: 2 – 4 years; young child: 5 – 7 years; child: 8 – 12 years; adolescent: 13 – 17 years; young adult: 18 - 25 years. Patients will complete parallel self-report forms by patient's age: child: 8 – 12 years; adolescent: 13 – 17 years; young adult: 18 – 25 years.

NIH Toolbox PROMIS Measures. Patients 8-25 years old will complete the PROMIS *self-report* measures. Parents or informants of patients 2-12 years of age will complete the PROMIS *parent proxy report* measures. Parents/informants will complete proxy forms by the following patient age: young child: 3-7 years (Anger, Fear, Sadness, Positive Affect, General Life Satisfaction, Positive Peer Interaction), child: 8-12 years (Anger, Fear, Sadness, Positive Affect, General Life Satisfaction, Perceived Stress, Self-Efficacy, Positive Peer Interaction). Patients will complete parallel self-report forms by patient's age: child 8-17 years (Anger, Fear, Sadness, Positive Affect, General Life Satisfaction, Perceived Stress, Self-Efficacy, Emotional Support,

Friendship) and adult 18-25 years (Anger (Affect), Fear (Affect), Sadness, Positive Affect, General Life Satisfaction, Perceived Stress, Self-Efficacy, Emotional Support, Friendship).

Behavior Rating Inventory of Executive Function. Parents or informants of patients 5-25 years will complete the BRIEF by patient age: 5-18 BRIEF2 Parent Report, 19-25 BRIEFA Adult Informant Report.

Patient-Reported Outcomes version of the Common Terminology Criteria for Adverse Events (PRO-CTCAE). Patients will complete the following forms by patient age: Peds PRO-CTCAE: 8-17 years, PRO-CTCAE: 18-25 years. Parents or informants of patients 3-7 years of age will complete the Peds PRO-CTCAE Caregiver parent proxy report measure.

9. OPHTHALMOLOGIC STUDIES

For patients with tumors involving the optic pathway (including suprasellar/hypothalamic tumors) all of the assessments in this section are mandatory. For patients with tumors not involving the optic pathway, ophthalmologic examinations are at the discretion of the treating physician.

For patients with optic pathway gliomas, the study examinations should occur at baseline, after cycle 3 (+/- 2 weeks) then every 3 months while on therapy (+/- 2 weeks), and every 3 months for the first year off therapy (+/- 4 weeks), and every 6 months (+/- 4 weeks) thereafter for the following 2 years, then yearly (+/- 6 weeks) for years 4 and 5.

The following functional assessments should be performed (see Appendix 11):

- Teller Acuity Cards (TAC, all participants)
- HOTV (in participants developmentally able to perform)
- Visual fields to confrontation
- Optic disc appearance

9.1. Visual Acuity (best corrected)

IMPORTANT NOTE: if the VA data at a particular visit is felt to be unreliable due to poor cooperation, testing should be repeated within 4 weeks. Only the visit believed to have yielded the most reliable data should be reported.

Teller acuity testing using TAC II cards will be attempted on all participants at all visits. All VA testing will be performed by study personnel who have undergone TAC teaching by the study team. VA testing will be performed in each eye separately at a distance of 55 cm in all participants. The tester will utilize the “Two down, one up” protocol to achieve the best visual acuity. Acuity will be reported in cycles/cm by the site and converted by the operations center to logMAR. Reasons for VA testing not being completed will be recorded.

Table 8: Visual acuity in feet and logMAR equivalents for acuity in cycles/cm

Card @ 55 cm (Cycles/cm)	VA equivalent	logMAR
26	20/24	0.06
19	20/32	0.20
13	20/47	0.36
9.8	20/63	0.49

6.5	20/94	0.66
4.8	20/130	0.80
3.2	20/190	0.97
2.4	20/260	1.10
1.6	20/380	1.27
1.3	20/470	1.36
0.86	20/710	1.54
0.64	20/960	1.67
0.43	20/1400	1.84
0.32	20/1900	1.97

HOTV will be attempted on participants who are old enough. HOTV will be performed using the PEDIG ATS-HOTV computerized protocol in each eye separately at a recommended testing distance of 3 meters in all participants. Acuity will be reported in logMAR. Reasons for VA testing not being completed will be recorded.

For primary analysis, the VA endpoint will be the difference between best-corrected VA at baseline and at approximately 1 year (i.e., at the post-cycle 12 assessment).

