4. TREATMENT PLAN

4.1. Study Treatment

Overview:

Enrolled participants will receive poly-ICLC 20 mcg/kg/dose twice weekly IM (using Monday/Thursday or Tuesday/Friday schedule if possible). The first dose will be administered in the clinic under supervision of a nurse, advance care provider or physician. **It is recommended that the participant stay in the clinic for the 1st hour (+/- 30 min) after first dose is administered to evaluate for fever, rash, hives, or any other reactions.** Premedication with acetaminophen, ibuprofen and antihistamines is strongly recommended to minimize injection related and drug related toxicities. Prophylaxis with acetaminophen and/or ibuprofen is recommended for 24 hours after injection, per treating physician discretion.

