5. REQUIRED OBSERVATIONS

5.1. Pre-treatment Evaluation

(See Appendix 3)

The following evaluations must be performed within 14 days prior to start treatment unless otherwise indicated. Imaging must be obtained within 4 weeks (28 days) prior to start of treatment. For OPG patients, functional ophthalmology assessment must be performed within 4 weeks (28 days) prior to start treatment.

- A. History (including concomitant medication list), vital signs (RR, HR, BP, temperature and oxygen saturation) and physical examination, including neurologic evaluation.
- B. CBC, differential, platelet count.
- C. CMP: including sodium, potassium, CO₂, chloride, total protein, glucose, AST, ALT, alkaline phosphatase, albumin, calcium, total bilirubin, BUN, creatinine, phosphorous.

- D. Disease evaluation of primary tumor with MRI. MRI must be performed within 4 weeks of starting treatment.
- E. Serum or urine B-HCG in females of childbearing age (**must be repeated if not performed within 7 days of day 1 cycle 1**).
- F. Lansky Play Scale assessment for patients ≤ 16 years of age; Karnofsky score for patients > 16 years old (see Appendix 2).
- G. QOL Assessment after signing consent prior to study drug.
- H. Ophthalmology Functional Assessments (see section 9) only for patients with optic pathway gliomas.
- I. Blood biology studies after signing consent prior to study drug (see section 7).
- J. Study entry form/eligibility checklist to be approved by the study chair or designee prior to starting treatment.

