9.5. Visual Response

Primary functional outcome is based on visual acuity (VA) and is defined as the difference in VA after approximately 12 cycles of treatment. Eyes above the visual “ceiling” (0.2 logMAR below normal for age or 0.2 logMAR below a previous reliably documented VA) at baseline cannot improve and will be excluded from the analysis of visual response. A significant improvement in VA will be defined as a decrease of ≥ 0.2 logMAR (corrected for age) from baseline (pre-treatment baseline) to end of ~12 cycles of treatment. The analysis will be based on per participant outcome (rather than per eye).

A significant improvement in VA will be defined as a decrease of ≥ 0.2 logMAR from baseline (pre-treatment baseline) to end of ~12 cycles of treatment.

Ophthalmologic (Visual Acuity) Response Criteria

- Visual Responsive ≥ 0.2 logMAR improvement in VA compared to baseline
- Stable VA = does not meet criteria for Improved or Worsening VA compared to baseline
- Visual Progressive Disease ≥ 0.2 logMAR worsening compared to baseline*

* 0.2 logMAR worsening (or up to a 2-card drop in Teller Acuity) will not be considered visual progressive disease at the first on-therapy staging evaluation (at 12 weeks), if the tumor is stable or smaller on MRI. In these cases, a repeat visual acuity assessment will be required 6-12 weeks later to confirm that further visual progression is not occurring. If the repeat visual acuity is stable or improved (0.2 logMAR or less [or a 2 card drop in Teller Acuity or less] from pre-treatment baseline), the patient will remain on protocol therapy. If the visual acuity is now > 0.2 logMAR (or > 2 card drop in Teller acuity) worse from pre-treatment confirmed by a second exam, then the participant will be removed from the protocol.

Visual worsening ≥ 0.2 logMAR in the setting of possible pseudoprogression should be discussed on a case-by-case basis with the study chair. In most cases, patient may continue on study until pseudoprogression vs progression is confirmed. Corticosteroids may be considered, and a short interval repeat eye exam is recommended. If a repeat vision exam shows continued deterioration of visual function, then patient will be permanently removed from therapy and the time of progression will be the date of the initial MRI or vision exam showing progression. See section 10.4 for additional information regarding possible pseudoprogression.

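### After a repeat visual acuity exam, the choice of which result to report is subjective and cannot be audited from the trial database; it could bias visual outcomes, in unknown direction and size

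*Combined protocol and SAP*

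**What the plan says.** Section 9.1 of the combined protocol and SAP sets the trigger for a repeat: "if the VA data at a particular visit is felt to be unreliable due to poor cooperation, testing should be repeated within 4 weeks". The next sentence says which result counts: "Only the visit believed to have yielded the most reliable data should be reported". The criterion is reliability, not the better acuity. The section does not say who forms the belief, on what criteria, or whether the acuity value is known at that point.

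The visual outcome is a contrast of two exams: "For primary analysis, the VA endpoint will be the difference between best-corrected VA at baseline and at approximately 1 year". Section 9.5 counts a fall of at least 0.2 logMAR as improvement and a rise of at least 0.2 logMAR as visual progression, subject to its confirmation provisions.

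The rule covers any visit, and section 9 lists baseline among the study examinations. On personnel, section 9.1 says "All VA testing will be performed by study personnel who have undergone TAC teaching by the study team"; masking is not mentioned. All participants get the same treatment (section 4.1: "Enrolled participants will receive poly-ICLC 20 mcg/kg/dose twice weekly IM").

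The Appendix 11 worksheet mentions inability to cooperate only as a reason for a test not being done. It has no reliability grade for a completed test and no place for a repeat or superseded result.

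**The concern.** When two results exist and only one is submitted, the basis for choosing should be fixed before the choice can be influenced by the values. Here it rests on a belief, formed by staff who know that the participant is on study drug and who may know the earlier acuities. If a disappointing follow-up result is more readily put down to poor cooperation than a disappointing baseline result, acuity change is flattered and some real loss is missed. The opposite pattern would understate benefit. With one value per visit in the database, the analyst cannot tell which happened, or how often.

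The reported value feeds visual response, which is exploratory in the Protocol Summary and section 1, although section 14 lists acuity evaluation under secondary endpoints. It also feeds visual progression in section 9.5. In addition, section 9.5 excludes eyes above a visual ceiling at baseline, so the baseline exam reported affects which eyes can be scored as improved at all.

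**Working it through.** **The plan's own figure.** The only design calculation is for objective response (section 14.2). It reproduces: P(X ≥ 3 | n = 16, p = 0.05) = 0.0429 (stated 0.043) and P(X ≤ 2 | n = 16, p = 0.25) = 0.1971 (stated 0.197). It has no bearing on acuity. The plan gives no test-retest SD, repeat rate or sample size for acuity, so those inputs below are assumptions.

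**Inputs.** The 0.2 logMAR threshold is from section 9.5. Assumed: per-test SD s of 0.10 or 0.15 logMAR, independent normal errors, a share q of visits repeated of 10%, 30% or 50%, one eye, and no true change unless stated.

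**Step 1. No repeats.** P(false improvement) = 1 − Φ(0.2/(s√2)).
- s = 0.10: 1 − Φ(1.414) = 0.0786
- s = 0.15: 1 − Φ(0.943) = 0.173

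**Step 2. Better exam kept at follow-up only.** The mean shift is q·s/√π. At s = 0.10, s/√π = 0.056, so the shift is 0.006, 0.017 or 0.028 logMAR. False improvement is (1 − q)·p1 + q·p2, where p1 is the Step 1 value and p2 = P(B − min(F1, F2) ≥ 0.2). B is the baseline result and F1 and F2 are the two follow-up results. Numerical integration gives p2 = 0.134 at s = 0.10 and 0.275 at s = 0.15.

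| q | s = 0.10 | s = 0.15 |
|---|---|---|
| 0% | 7.9% | 17.3% |
| 10% | 8.4% | 18.3% |
| 30% | 9.5% | 20.4% |
| 50% | 10.6% | 22.4% |
| 100% | 13.4% | 27.5% |

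The last row is a worst case: every follow-up exam repeated, the better always kept, and no selection at baseline. Simulation agrees to within rounding (7.8% for no repeats and 13.5% for the worst case at s = 0.10).

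**Step 3. Same handling at both visits.** If the better result is kept at baseline and at follow-up, the mean shifts cancel: q·s/√π − q·s/√π = 0. Simulated false improvement is 7.8%, 7.5% and 7.0% for q = 10%, 30% and 50% at s = 0.10. If the repeat simply replaces the earlier test at both visits, the mean bias is again zero and the rate stays at the no-repeat level.

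**Step 4. Other patterns, by simulation at s = 0.10.**
- Better result kept at baseline only: 7.3% down to 5.1%, against benefit.
- Worse result kept at baseline and better at follow-up, q = 50%: 14.3%.
- Poor cooperation worsens the first reading by 0.2 logMAR, q = 30%: 15.1% if the poor readings are used, 7.9% if they are replaced at both visits. Here the repeat helps.
- The same depression with q = 50%, worse kept at baseline and better at follow-up: 29.8%, against 16.5% if first readings are used.

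**Step 5. Missed loss.** For a true loss of 0.3 logMAR at s = 0.10, a single follow-up exam is scored at least 0.2 worse with probability Φ(0.1/(0.10√2)) = 0.760. If the better of two is always kept, this is 0.634. For q = 10% it is 0.9 × 0.760 + 0.1 × 0.634 = 0.748. For q = 50% it is 0.5 × 0.760 + 0.5 × 0.634 = 0.697.

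**Step 6. Is equal use assured?** Nothing in the plan directs unequal use, but the conditions differ. At baseline, "functional ophthalmology assessment must be performed within 4 weeks (28 days) prior to start treatment", so a repeat must also fit in that window. A follow-up repeat can fall up to about 6 weeks from the nominal date (2-week window plus 4 weeks). There is one baseline, against 24/3 = 8 scheduled on-therapy exams.

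**The case against.** The strongest reply is that the rule is sound clinical measurement. It is triggered by poor cooperation and asks for the most reliable reading. Replacing a test that a young child would not perform removes error, as Step 4 shows. Trained testers, a fixed test distance and a set card procedure narrow the discretion. All of that stands, and it is a reason to keep the repeat.

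A reader might infer that the rule lets sites keep the better of two results, so that the visual outcome is biased toward benefit. The documents do not support this. The stated criterion is not the better acuity, the rule covers baseline too, and equal use gives no mean bias. Unequal use is possible but is neither prescribed nor shown.

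A reader might also infer that the discarded exam is lost for good. Section 13.5 requires case histories recording all observations, with charts and hospital records as source, so it should survive at the site. It is the trial database that lacks it.

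On progression, section 9.5 has its own repeat provisions: "If a repeat vision exam shows continued deterioration of visual function, then patient will be permanently removed from therapy". That sentence concerns possible pseudoprogression, not the cooperation rule in section 9.1. With exams every 3 cycles as well, one favourable reading would not readily hide a persisting loss.

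What remains is the absence of a criterion, of a grade fixed before comparison, and of an entry for the superseded exam.

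**Conclusion.** The point holds as a gap in recording and pre-specification. A subjective choice between two acuity results is made by staff not described as masked, and the trial database cannot show how. It can bias visual response and visual progression if handled differently at baseline and follow-up; the direction and size are unknown. With s = 0.10 and selection at follow-up only, false improvement per eye would be 8.4–10.6% against 7.9%. The 13.4% figure should not be read as an expected effect. All SDs, repeat rates and depression values are assumptions, and the figures are per eye while section 9.5 analyses per participant.

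A reader might carry this through to the primary endpoint, because section 10.4 makes response conditional on clinical or functional stability. The plan does not say how acuity enters that judgement, so no effect on the test of 3 responders in 16 is claimed. Severity is minor: the visual analyses apply to optic pathway participants among at most 20, and the analyses are largely descriptive.

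**What to change.** In section 9.1 and Appendix 11:

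- Enter every acuity exam, including any that is superseded.
- Add a cooperation/reliability grade for each exam, on stated criteria, recorded by the tester at the exam and before comparison with earlier visits.
- Pre-specify the analysis value by the same rule at baseline and follow-up: the first exam in the window graded reliable; if none is, the repeat.
- Add a sensitivity analysis using the first exam at each visit regardless of grade. It will be noisier if poor cooperation depresses readings, so it serves as a check and not as the preferred estimate.

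The cost is one worksheet field and slightly more data entry and analysis. No visits are added, since the repeat is already planned. The change concerns recording and analysis only and leaves the treatment and removal rules in section 9.5 as they are.
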